# 7.2 Sample Size

We expect at least 160 (120 in 744LA and 40 in placebo) out of 176 participants who will complete the primary endpoint visit (week 41) assuming the annual retention rate to be approximately 90%. The following power calculations are based on the sample size of 160 (120 in 744LA and 40 in placebo).

The goal of the safety evaluation for this study is to identify safety concerns associated with 744LA. The ability of the study to detect SAEs (See Section 6.3) can be expressed by the true event rate above which at least 1 SAE would likely be observed and the true event rate below which no events would likely be observed. Specifically, for the 744LA arm of the study (n =120), there is a 90% chance of observing at least 1 event if the true rate of such an event is 2% or more, and there is a 90% chance of observing no events if the true rate is <0.1%. For the placebo arm (n=40), there is a 90% chance of observing at least 1 event if the true rate of such an event is 5.6% or more, and there is a 90% chance of observing no events if the true rate is 0.2% or less.

Probabilities of observing 0, 1 or more, and 2 or more events among the arms (N=160; 120 in 744LA arm, and 40 in placebo arm) are presented in Table 3 for a range of true adverse event rates. These calculations provide a more complete picture of the sensitivity of this study design to identify potential safety concerns with 744LA.

Table 3: Probability of observing 0 events, 1 or more events, and 2 or more events, among both arms: the 744LA arm (n=120) and the placebo arm (n=40), for different true event rates.

True event						
rate (%)	Pr(0/120)	Pr(1+/120)	Pr(2+/120)	Pr(0/40)	Pr(1+/40)	Pr(2+/40)
0.5	54.8	45.2	12.2	81.8	18.2	1.7
1	29.9	70.1	33.8	66.9	33.1	6.1
2.5	4.8	95.2	80.5	36.3	63.7	26.4
5	0.2	99.8	98.4	12.9	87.1	60.1
10	< 0.1	>99.9	>99.9	1.5	98.5	92
15	< 0.1	>99.9	>99.9	0.2	99.8	98.8

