The primary safety endpoint is the proportion of participants experiencing any Grade 2 or higher clinical AEs and laboratory abnormalities that occur from the initial injection to 41 weeks among participants who receive at least one injection. The precision with which the true event rate can be estimated from the observed data depends on the underlying true event rate and the sample size. Table 4 shows the two-sided 95% confidence intervals for the true event rate based on various values for the observed event rates, given the sample size of 120 in 744LA arm and 40 in placebo arm. Calculations are done using the score test method.

Table 4. Two-sided 95% confidence intervals based on observing a particular rate of event for the 744LA arm (n=120) and the placebo arm (n=40)

Observed Event	95% CI (744LA arm)	95% CI (Placebo arm)
Rate (%)		
0	(0, 3.1)	(0, 8.8)
2.5	(0.9, 7.1)	(0.4, 12.9)
5	(2.3, 10.5)	(1.4, 16.5)
10	(5.8, 16.7)	(4, 23.1)
15	(9.7, 22.5)	(7.1, 29.1)
20	(13.8, 28)	(10.5, 34.8)
25	(18.1, 33.4)	(14.2, 40.2)

The safety and toxicity rates of people using 744LA and the rates for those using placebo will not be formally compared. A sample size of 160 participants (120 in 744LA and 40 in placebo) assuming 90% retention rate per year will assure with 82% power that a 95% confidence interval for the difference between the study drug and placebo safety and toxicity rates has an upper limit no more than 10% when the true toxicity rates for 744LA and placebo are both 5%. Table 5 displays two-sided 95% confidence interval for different assumptions on the safety and toxicity rates in the active product and placebo arms for a study of this sample size.

Table 5: Two-sided 95% Confidence Intervals for the Difference between 744LA and Placebo Safety Rates (n=120 in the 744LA arm and n=40 in the placebo arm)

Assumed rate	Assumed rate in 744LA arm											
in placebo arm	1% 5%		7.5%	10.0%	12.5%	15.0%						
1%	(-3.6, 3.6)	(-1, 9)	(0.9, 12.1)	(2.8, 15.2)	(4.8, 18.2)	(6.9, 21.1)						
5%	-	(-7.8, 7.8)	(-5.7, 10.7)	(-3.6, 13.6)	(-1.5, 16.5)	(0.7, 19.3)						
7.5%	-	1	(-9.4, 9.4)	(-7.3, 12.3)	(-5.1, 15.1)	(-2.9, 17.9)						
10.0%				(-10.7,	(05.105)	( ( 2 1 ( 2 )						
	-	-	-	10.7)	(-8.5, 13.5)	(-6.3, 16.3)						
12.5%					(-11.8,							
12.5 /0	-	-	-	-	11.8)	(-9.6, 14.6)						
15.0%						(-12.8,						
15.0 / 0	-	-	-	-	-	12.8)						

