# 7.4 Random Assignment

Enrolled participants will be assigned 3:1 at random to one of two study arms stratified by gender. The randomization scheme will be generated, operationalized and maintained by the HPTN SDMC. Additional details regarding the process of randomization will be included in the SSP Manual.

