# **Safety Endpoints**

The primary safety analysis will include Grade 2 or higher clinical and laboratory events that occur from the initial injection to 12 weeks after the last injection among participants who receive at least one injection. Secondary safety analyses will include the same definition applied over the oral phase only (week 0 to week 5) and the aggregate oral+injectable+follow-up period.

To assess safety, the number and the percent of participants experiencing each safety endpoint will be tabulated by study arm. Each participant will contribute once in each category (for example, only for the highest severity AE for each participant) for the calculation of event rates. Exact binomial confidence intervals will be calculated for each safety endpoint for each arm and Fisher's exact test used to test for differences in event rates between the two arms. No formal treatment comparisons will be performed in this study, so any p-values that are calculated should only be used as a descriptive statistic. No formal multiple comparison adjustments will be employed for safety endpoints.

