### **Tolerability**

To assess tolerability, the number and the percent of participants who receive at least one injection and discontinue receiving injections prior to the full course due to intolerability of injection (including but limited to ISR), frequency of injections, or burden of procedures or any AE will be tabulated by study arm. Chi-square test will be used to compare the proportion of participants who terminated from receiving the full course of injections due to any of the above reasons between the two study arms.

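### The only power statement and Table 5 concern a confidence interval for the arm difference, which the methods fixed in 7.6.2 never produce; Table 5's own intervals reproduce as Wald intervals, which cover 87.8% at the planning rates

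*Protocol*

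**What the plan says.** **Planning (Protocol 7.2).** The evaluable numbers are 120 on 744LA and 40 on placebo. The section's one power statement is that this size "will assure with 82% power that a 95% confidence interval for the difference between the study drug and placebo safety and toxicity rates" will have an upper limit of at most 10 points when both true rates are 5%. Table 5 lists two-sided 95% intervals for the difference over a grid of rates and does not name the method. The per-arm intervals in Table 4 do have a named method: "Calculations are done using the score test method". Table 3 adds the probabilities of seeing 0, at least 1 and at least 2 events in each arm.

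**Analysis (Protocol 7.6.2).** Under Safety Endpoints: "Exact binomial confidence intervals will be calculated for each safety endpoint for each arm", with Fisher's exact test between arms and any p-values to be read as descriptive. Under Tolerability: "Chi-square test will be used to compare the proportion of participants" who stop injections early. The general paragraph of 7.6.2 also lists logistic regression and exact methods for cases where formal testing is required, but ties neither to a primary endpoint. No interval for the arm difference appears.

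**Randomisation (Protocol 7.4).** Participants are "assigned 3:1 at random to one of two study arms stratified by gender". No between-arm method in 7.6.2 mentions gender.

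**The concern.** The protocol does not leave this open. It fixes an analysis method for each primary endpoint, and what it fixes does not match what section 7.2 plans for. The planning quantity, "a 95% confidence interval for the difference between the study drug and placebo safety and toxicity rates", is not among the results that 7.6.2 will deliver. The protocol also says that the arms will not be formally compared, yet the only between-arm results it fixes for these endpoints are test p-values. A descriptive comparison calls for an estimate with its uncertainty, all the more with 40 placebo participants.

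Two misreadings are at stake. A large Fisher p-value may be taken to show no excess risk when the data still allow an excess of almost 20 points. In the other direction, someone who takes Table 5 as a guide to what the trial could show will expect a difference of 15% against 5% to exclude zero, when a better interval does not.

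**Working it through.** **Inputs.** n1 = 120 (744LA) and n0 = 40 (placebo); true rates 5% and 5%; upper-limit criterion 10 points; two-sided 95% intervals. All are from 7.2.

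**Step 1: reproduce Table 5.** The unpooled Wald interval is (p1 - p0) ± 1.96·√[p1(1 - p1)/120 + p0(1 - p0)/40].

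- 5% against 5%: √(0.0475/120 + 0.0475/40) = √0.001583 = 0.0398. Times 1.96 this is 0.078, so -7.8 to 7.8, as printed.
- 15% against 5%: √(0.1275/120 + 0.0475/40) = √0.00225 = 0.0474. Times 1.96 this is 0.093, so 10 ± 9.3, that is 0.7 to 19.3, as printed.

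The other legible entries agree to 0.1 point.

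**Step 2: reproduce the 82%.** Enumerate every pair of counts (x1, x0), weight each by the two binomial probabilities at 5%, and add the weights of pairs whose interval has an upper limit of at most 10 points. The Wald interval gives 82.4%, against the stated 82%.

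**Step 3: coverage.** The same enumeration gives the chance that the interval contains the true difference.

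| True rates (744LA/placebo) | Wald | Newcombe |
|---|---|---|
| 5%/5% | 87.8% | 97.0% |
| 7.5%/7.5% | 91.7% | 96.0% |
| 10%/10% | 92.8% | 95.3% |
| 15%/5% | 94.3% | 95.7% |
| 15%/15% | 93.6% | 95.2% |

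The 5%/5% cell is the lowest on the Table 5 grid; the others run from 91.7% to 97.8%. The Wald error at 5%/5% is lopsided: the lower limit lies above the true difference in 11.5% of trials and the upper limit lies below it in 0.7%, against a nominal 2.5% each. One source is zero placebo events, which has probability 0.95^40 = 12.9%. Then 4 events among 120 on 744LA already put the Wald lower limit above zero (0.1 to 6.5 points), while Fisher's p-value for those data is 0.57.

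**Step 4: what this does to one Table 5 cell.** The 15% against 5% entry corresponds to 18/120 and 2/40. Newcombe's interval can be built from the score limits printed in Table 4: 9.7 to 22.5 for 15% of 120, and 1.4 to 16.5 for 5% of 40. In points:

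- Lower limit: 10 - √[(15 - 9.7)² + (16.5 - 5)²] = 10 - √160.3 = -2.7.
- Upper limit: 10 + √[(22.5 - 15)² + (5 - 1.4)²] = 10 + √69.2 = 18.3.

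The Miettinen-Nurminen interval is -2.5 to 18.7. Both include zero, and Table 5's does not. Fisher's test on the same counts gives p = 0.16, which by itself does not show that an excess of about 18 points remains possible.

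**Step 5: does the planning claim survive a better interval?** At 5%/5% the chance of an upper limit of at most 10 points is 83.0% with Miettinen-Nurminen (coverage 96.0%) and 83.5% with Newcombe (coverage 97.0%). It survives.

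**Step 6: the per-arm intervals.** At 15% observed, n = 40, score gives 7.1 to 29.1 and exact gives 5.7 to 29.8. Over all of Table 4 the limits differ by at most 0.6 point for 744LA and 1.5 points for placebo.

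**The case against.** The strongest defence is that the trial estimates safety arm by arm. Section 7.2 sets the goal of finding safety concerns with 744LA, supports it with Table 3, and ties the primary safety endpoint to per-arm precision in Table 4. The 82% sentence comes directly after the statement that the arms will not be formally compared, and 7.6.2 declares its safety p-values descriptive. On that view nothing turns on the missing interval. Part of this stands: planning does not rest on the difference alone, and Fisher's low power (35% at 15% against 5%) and small actual size (2.7% at 5%/5%) feed no decision rule. But a protocol that states a power for an interval and tabulates it should report that interval, and calling a comparison descriptive is a reason for an estimate rather than a p-value.

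Several stronger readings are tempting and are not supported:

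- **The planning interval has 88% coverage in general.** That figure belongs to 5%/5%. The rates for the primary safety endpoint may well be higher: section 1.4 reports Grade 2 injection site reactions alone in 14% after intramuscular dosing.
- **The trial is too small or the 82% is wrong.** The criterion uses the upper limit, which is conservative at 5%/5%.
- **The final analysis will use a Wald interval.** Nothing commits it to one.
- **The crude comparison is biased because it ignores gender.** Randomisation was stratified by gender, so differing gender mixes across sites do not bias it. Adjustment improves a descriptive summary and may be left to the SAP.
- **Fisher and chi-square must go.** With an expected placebo count of 2 (assuming 5% discontinuation) the chi-square approximation is rough, but its actual size at 5%/5% is 4.0%, not inflated, and the general paragraph of 7.6.2 allows exact methods.
- **Exact per-arm intervals are wrong.** They are valid; the issue is only that the two sections differ.

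**Conclusion.** The point holds as a mismatch between planning and analysis: the methods fixed for the two primary endpoints do not yield the interval to which the protocol's only power statement refers. It should be corrected, but it does not threaten the design.

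Its size is as follows. Table 5 is unreliable in its lower limits when placebo events are few: coverage is 87.8% at 5%/5%, with 11.5% of lower limits too high. At least one entry, 15% against 5%, excludes zero where score-type intervals for the matching counts do not. The 82% figure becomes 83.0% to 83.5%, so it and the sample size stand. The change of per-arm method from score to exact is an inconsistency worth at most 1.5 points.

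This rests on 120 and 40 evaluable participants, on independent binomial counts, and on the inference that Table 5 uses the unpooled Wald formula. The table names no method, but its legible entries match that formula to 0.1 point. A reader might infer that the trial's safety conclusions would be invalid as planned. The documents do not support that, because the per-arm proportions with 95% intervals are provided for.

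**What to change.** 1. In 7.6.2, for both primary endpoints, give the risk difference (744LA minus placebo) with a two-sided 95% score-type interval, Miettinen-Nurminen or Newcombe, as the between-arm summary, preferably stratified by gender because that is the randomisation factor.
2. Recompute Table 5 with the chosen interval and name the method beside the table and the 82% sentence, updating the figure to 83.0% (Miettinen-Nurminen) or 83.5% (Newcombe).
3. Keep any Fisher or chi-square p-values secondary, and describe them as descriptive for both endpoints.
4. Use the same per-arm interval in 7.2 and 7.6.2. Either score or exact is acceptable.

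The cost is a few lines of analysis text and one recomputed table, with no change to sample size, visits or data collection. The downside is a less favourable lower limit in some cells, as at 15% against 5%. If score is chosen for the per-arm intervals, the guarantee of at least 95% coverage that exact intervals carry is given up.

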# **Injection Site Reaction (ISR)**

The number and percentage of participants experiencing each type of injection site reaction sign or symptom will be tabulated by severity. For a given sign or symptom, each participant's ISR will be counted once under the maximum severity for all injection visits as well as by each successive injection.

#### **AEs**

AEs will be tabulated using MedDRA preferred terms. The number and percentage of participants experiencing each specific AE (All AEs, Grade 2 or higher, and SAEs) will be tabulated by severity and by relationship to study product. For the calculations in these tables, each participant's AEs will be counted once as the maximum severity and relationship to study product. AEs leading to temporarily or permanently stopping drug will also be summarized by treatment. AEs will be summarized for those that are treatment emergent during LA dosing separately from those that are treatment emergent during oral dosing and also for those that are treatment emergent across the entire treatment phase of the study (combining both LA and oral dosing).

A listing of EAEs reported to the DAIDS RSC Safety Office will provide details of the events including severity, relationship to study product, time between onset and last injection, number of injections received, and a summary of the event.

### **Tolerability**

To assess tolerability, the number and the percent of participants who receive at least one injection and discontinue receiving injections prior to the full course due to intolerability of injection (including but limited to ISR), frequency of injections, or burden of procedures or any AE will be tabulated by study arm. Chi-square test will be used to compare the proportion of participants who terminated from receiving the full course of injections due to any of the above reasons between the two study arms.

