## 3.5 Participant Retention

Once a participant enrolls in this study, the study site will make every effort to retain him or her for the entire follow-up period. Optimally, participant retention procedures will be established such that loss rates do not exceed the range that allow the incidence rate of the primary study outcome to be reliably estimated (i.e., a maximum of 10% as assumed in the sample size calculation). Study site staff are responsible for developing and implementing local standard operating procedures to target this goal. Components of such procedures may include:

- Thorough explanation of the study visit schedule and procedural requirements during the informed consent process and re-emphasis at each study visit.
- Thorough explanation of the importance of both arms to the overall success of the study.
- Collection of detailed locator information at the study Screening Visit, and active review and updating of this information at each subsequent visit, including where the participant lives and other locator venues.
- Use of appropriate and timely visit-reminder mechanisms.
- Immediate and multifaceted follow-up on missed visits.
- Mobilization of trained staff to complete in-person contact with participants at their homes and/or other community locations.
- Regular communication with the study community at large to increase awareness about HIV/AIDS and explain the purpose of HIV prevention research and the importance of completing research study visits.

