# 7.1.1 Primary Endpoint

Safety endpoint: Proportion of participants experiencing any Grade 2 or higher clinical AEs and laboratory abnormalities that occur from the initial injection to Week 41 among participants who receive at least one injection (injectable phase only)

Tolerability endpoint: Proportion of participants who receive at least 1 injection and who discontinue receiving injections prior to the full course of 3 injections due to intolerability of injection (including but not limited to ISR), frequency of injections, burden of study procedures, or any AE.

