The tolerability of 744LA will be measured by the proportion (with 95% CI) of participants who terminate from receiving injections prior to the full course due to AE, intolerability of injection, frequency of injections, or burden of procedures related to injections out of those subjects that received at least one injection by treatment arm. Table 4 shows two-sided 95% confidence intervals for true tolerability rate based on various possible observed rates, given the sample size of 120 participants in the 744LA arm.

The acceptability of 744LA will be measured by the proportion (with 95% CI for the 744 LA arm) of participants who would consider using 744LA for HIV prevention in the future. This endpoint will be measured at the end of the study on every enrolled participant (including those who terminated product use during the trial). Table 6 shows two-sided 95% confidence intervals for true acceptance rate based on various possible observed rates, given the sample size of 120 participants in the active 744LA arm

Table 6: 95% Confidence Intervals for the True Acceptance Rate Given Possibly Observed Rates

N	Observed Event Rate	95% CI for True Event Rate
	50%	(41.2%, 58.8%)
	70%	(61.3%, 77.5%)
Arm 1: 120 (744LA)	80%	(72%, 86.2%)
	90%	(83.3%, 94.2%)
	95%	(89.5%, 97.7%)

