# 7.6.2 Primary Analyses

All participants who receive at least one injection will contribute to the primary analyses.

When the use of descriptive statistics to assess group characteristics or differences is required, the following methods will be used: for categorical variables, the number and percent in each category; for continuous variables, the mean, median, standard deviation, quartiles and range (minimum, maximum). Within-treatment group assessment of the change from the baseline measurement to a follow-up measurement will be analyzed using McNemar test (for categorical response variables) or the paired t-test or Wilcoxon signed-ranks test (for continuous variables). When use of formal testing to assess differences between users of the placebo arm and users of 744LA is required, the following methods will be used: for binomial response variables, chisquare tests and logistic regression (or exact testing methods); for continuous variables, t-tests and linear regression or nonparametric methods if data are non-normal.

To assess the adequacy of the randomization, participants in each of the two arms will be compared for baseline characteristics including demographics and laboratory measurements using descriptive statistics only.

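### The primary tolerability proportion scores participants who are lost or leave without a recorded reason before the third injection as non-events, so for that group it is a lower bound and can be understated.

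*Protocol*

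**What the plan says.** Section 7.1.1 defines the tolerability endpoint as the proportion of participants with at least one injection who "discontinue receiving injections prior to the full course of 3 injections due to intolerability of injection (including but not limited to ISR"), injection frequency, burden of study procedures, or any AE. Under Tolerability, Section 7.6.2 repeats the definition: "participants who receive at least one injection and discontinue receiving injections prior to the full course due to intolerability of injection", then "frequency of injections, or burden of procedures or any AE will be tabulated by study arm". Its parenthesis on injection site reactions, however, lacks the word *not* that Section 7.1.1 has.

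The denominator is fixed in two places. Section 7.2 takes the proportion "out of those subjects that received at least one injection by treatment arm", and Section 7.6.2 opens with "All participants who receive at least one injection will contribute to the primary analyses". No rule treats participants lost before the third injection differently.

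The discontinuation endpoint in Section 7.1.2 is also limited by reason (toxicity, tolerability or acceptability). The protocol specifies no all-cause proportion for not completing the injections.

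On losses, Section 7.2 plans the sample size "assuming the annual retention rate to be approximately 90" per cent, and Section 3.5 speaks of "a maximum of 10% as assumed in the sample size calculation".

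**The concern.** The numerator depends on a reason and the denominator does not. Someone who has the Week 5 injection, stops attending and gives no reason enters the estimate exactly as someone who had all three injections. If some of these people stopped because they could not tolerate the injections, they are misclassified, and always in the direction of better tolerability.

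This kind of departure is foreseeable. Section 3.6 and Appendix VI allow participants to leave the study or stop product for any reason at any time. Appendix VI also lists the participant's own request as a ground for permanent discontinuation, and a bare request is not one of the endpoint's listed reasons.

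This is one of two primary endpoints, and the planned loss over the injection period is about as large as a 5% event rate. A reader given only the reason-based figure cannot tell how far it depends on whether reasons were obtained.

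**Working it through.** **Inputs**
- Retention of 90% per year (Sections 7.2 and 7.3).
- Injections at Weeks 5, 17 and 29 (Sections 2.4 and 4.1), so 24 weeks from first to third.
- n = 120 on 744LA and 40 on placebo. Section 7.2 uses n = 120 for tolerability precision.
- Two-sided 95% score intervals (Section 7.2, Table 4).

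**Step 1. Reproduce the plan's interval.** The score interval is [p + z²/2n ± z√(p(1−p)/n + z²/4n²)] / (1 + z²/n), with z = 1.96.
- For p = 0.05 and n = 120, the centre is (0.05 + 0.0160)/1.0320 = 0.0640.
- The half-width is 1.96 × √(0.000396 + 0.0000667)/1.0320 = 0.0408.
- The interval is 2.3 to 10.5%, as in Table 4. All 14 intervals in Table 4 reproduce to one decimal.

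**Step 2. Loss between the first and third injection.** Assuming a constant loss rate, 1 − 0.9^(24/52) = 4.75%.
- 744LA: 0.0475 × 120 = 5.7, about 6. With all 132 randomised it is 6.3, so the choice of n hardly matters.
- Placebo: 0.0475 × 40 = 1.9, about 2.

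This is a ceiling for unexplained departures at the planned retention. It also includes people who gave a listed reason and are already events, and people with a documented unrelated reason.

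**Step 3. Three ways to treat the lost**

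| Arm, listed-reason stops, lost | Protocol rule | Lost removed from denominator | All lost counted as events |
|---|---|---|---|
| 744LA, 3/120, 6 lost | 2.5% (0.9–7.1) | 2.6% (0.9–7.5) | 7.5% (4.0–13.6) |
| 744LA, 6/120, 6 lost | 5.0% (2.3–10.5) | 5.3% (2.4–11.0) | 10.0% (5.8–16.7) |
| 744LA, 12/120, 6 lost | 10.0% (5.8–16.7) | 10.5% (6.1–17.5) | 15.0% (9.7–22.5) |
| Placebo, 2/40, 2 lost | 5.0% (1.4–16.5) | 5.3% (1.5–17.3) | 10.0% (4.0–23.1) |

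The third column represents the case where the lost are like those retained: 6/114 = 5.3%, a gap of about 0.3 points. The last column is the worst case.

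**Step 4. Between the extremes.** Each intolerant participant recorded only as lost adds 1/120 = 0.83 points. If a quarter of the six were intolerant, 5.0% becomes (6 + 1.5)/120 = 6.25%. If half were, it becomes 7.5%.

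**The case against.** The other side has a good deal of weight.

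- **The endpoint is legitimate and bounding is often left to the SAP.** A reason-based discontinuation proportion is a fair choice, and sensitivity analyses commonly sit in the SAP, which is not shown. That holds for imputation detail. Here, though, the protocol itself fixes the numerator and denominator of a primary endpoint, and an added SAP analysis would not change what the primary figure means.
- **The affected group is small.** The reasons are broad, and Sections 3.6 and 5.23 require withdrawal reasons to be recorded. Participants who stop injections are followed for 52 weeks after their last one (Section 5.15), and missed injection windows go to the CMC (Section 5.13). This stands and shrinks the group to those who vanish or give no reason.
- **Other tabulations help.** Injection site reactions are summarised by severity and by injection, and AEs leading to stopping are summarised. These reduce reliance on the endpoint but do not bound it.

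Several stronger readings are tempting and not supported:

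- *That intolerability is understated.* This needs some silent leavers to have been intolerant, and the protocol gives no such share. Nor does it say that people commonly leave silently because injections are painful. Section 1.4 reports one AE withdrawal among 136 subjects given 744LA, and Appendix V says that injection site reactions had not led to withdrawal.
- *That every unlisted stop is misclassified.* Documented stops for pregnancy or a wish for it, HIV infection or changed risk status are correctly non-events.
- *That the endpoint as a whole can err only downward.* Any AE counts, related or not, so some events may have nothing to do with tolerating the product. The one-way argument covers only the unexplained leavers.
- *That the rate doubles.* That is the worst case, in which all six lost were intolerant.

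**Conclusion.** The point holds in a limited form. As defined in Sections 7.1.1, 7.2 and 7.6.2, the primary tolerability proportion is a lower bound with respect to participants lost or leaving without a recorded reason before the third injection. It can be understated, but the documents do not show that it will be.

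At an observed 5% on 744LA, the possible understatement is 0 to about 5 points, and about 0.3 points if the lost resemble those retained. This rests on three assumptions: the 90% annual retention, a constant rate of loss, and treating all loss between Weeks 5 and 29 as unexplained. The last makes the upper end a ceiling. If the full 10% of Section 3.5 fell between the first and third injections (12 of 120), the worst case would be (6 + 12)/120 = 15.0% (9.7 to 22.5%).

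The trial is Phase IIa, its safety and toxicity rates are not formally compared, and no tolerability threshold is set. This is therefore an inexpensive improvement to how a primary endpoint is reported, not a flaw that invalidates it.

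**What to change.** In Section 7.6.2, under Tolerability:

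1. Keep the reason-based proportion as primary.
2. Add a bounding sensitivity proportion, by arm with a 95% CI and on the same denominator. It also counts as events participants lost or withdrawn without a documented reason before the third injection. Stops for documented non-tolerability reasons stay non-events.
3. When concluding on tolerability, describe the primary figure as a lower bound with respect to unexplained departures.
4. Reconcile the wording on injection site reactions in Section 7.6.2, which lacks *not*, with Section 7.1.1, because it affects which reasons count.

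The cost is a few lines of text and one table column, using withdrawal reasons that sites already have to record. The downside is that the added figure is conservative, since some unexplained departures will have nothing to do with the product.
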